### 13.1 Adverse Events

An AE is defined as any untoward medical occurrence associated with the use of a drug in humans, whether or not the event is considered drug-related. An AE can therefore be any unfavorable and unintended sign (eg, an abnormal laboratory finding), symptom, or disease occurring after the first dose of study drug, without any judgment about causality. Any pre-existing medical condition that worsens after first administration of the study drug will also be considered a new AE. The AE reporting period starts from the time the subject signs the informed consent until the subject's last study visit. All AEs will be coded using MedDRA Version 23.0.

A treatment-emergent adverse event (TEAE) is defined as any event that occurs or worsens on or after the first dose of study medication. Adverse events recorded on the eCRF which began prior to treatment and remained unchanged or improved will not be included in the summary tables but will be included in the AE data listings. For all AE summary tables, a third group other than QD and BID dose group will be presented to capture the AEs for those subjects who switched the treatment dose from QD to BID starting from Week

4. The AE that began on or after the switch will be considered treatment emergent to the BID treatment; The AE that began before the switch and continued after the switch will be considered treatment emergent to the QD treatment only; if the AE worsened on or after the switch, the new AE (one with higher severity) would become a TEAE for the BID dose and the original AE would be treatment emergent to the QD dose.

An overall summary will be presented that includes the number of events and the number and percentage of subjects who experienced at least one TEAE, by treatment group. This summary will also include breakdowns of TEAEs further categorized as ocular (study eye and fellow eye separately with TEAEs occurred on both eyes counted towards study eye once and fellow eye once) or non-ocular, TEAEs by maximum severity, TEAEs by maximum relationship to study medication, TEAE by expectedness, serious TEAEs, TEAEs leading to study medication discontinuation, TEAEs leading to death.

Additional summaries of TEAEs will be provided showing the number and percentage of subjects who experienced at least one TEAE by treatment group. Non-ocular TEAEs will be summarized using discrete summary statistics and presented by treatment group at the subject level by SOC and PT. Ocular TEAEs will be summarized similarly at the subject level for study eyes and fellow eyes, separately. If a subject reports the same PT multiple times within the same SOC, that PT will only be reported once within that SOC. As with the PT, if a subject reports multiple conditions within the same SOC, that SOC will only be reported once. In the summary, SOCs and PTs within each SOC will be listed in ascending alphabetical order.

Separate summaries will be provided for the following categories of AEs:

- Ocular TEAEs in the study eye and fellow eye
- Non-ocular TEAEs
- Ocular TEAEs related or possibly related to study medication
- Non-Ocular TEAEs related or possibly related to study medication
- Serious TEAEs
- Serious TEAEs related or possibly related to study medication

Severity of an AE is defined as a qualitative assessment of the level of discomfort or the degree of intensity of an AE as determined by the Investigator or reported to him/her by the subject. The assessment of severity is made irrespective of study medication relationship or seriousness of the event and should be evaluated according to the following scale:

- Mild: Present and noticeable, but not distressing, and no disruption of normal daily activities.
- Moderate: Bothersome, discomfort sufficient to possibly reduce or affect normal daily activity.
- Severe: Incapacitating, with inability to work or perform normal daily activity.

A change in increased severity for a reported AE will require a stop date for the previous severity and a new start and stop date for the new severity. For example, a change in severity may go from mild to severe or from moderate to severe. In both cases, the start and stop dates should be recorded.

The relationship of each AE to the study drug should be determined by the Investigator using these explanations:

- **Not Related:** The event is clearly related to other factors such as subject's clinical condition; therapeutic interventions, concomitant disease or therapy administered to the subject and does not follow a known response pattern to the product.
- **Unlikely Related:** The event is most probably caused by other etiologies such as participant's underlying condition, therapeutic intervention, or concomitant therapy; or the delay between administration and the onset of the AE is incompatible with a causal relationship. Therefore, there is not a reasonable possibility that the AE was caused by the study medication.
- **Possibly Related:** The event follows a reasonable, temporal sequence from the time of study medication administration and/or follows a known response pattern to the study medication, but could have been produced by other factors such as the subject's clinical state, therapeutic interventions or concomitant therapy administered to the subject.
- **Related:** The event follows a reasonable, temporal sequence from the time of study medication administration and/or follows a known response pattern to the study medication and cannot be reasonably explained by other factors such as subject's clinical state, therapeutic interventions or concomitant therapy administered to the subject, and either occurs immediately following study medication administration, or improves on stopping the study medication, or reappears on repeat exposure, or there is a positive reaction at the application site.

Summaries of TEAEs by maximum severity will be presented for ocular TEAEs and non-ocular TEAEs separately. The number of subjects with any TEAEs (along with percentages) will be tabulated by SOC and PT within each SOC by treatment group. To count the number of subjects with any TEAEs, if a subject has multiple TEAEs coded to the same PT within the same SOC, the subject will be counted once under the maximum severity.

Individual subject listing will be provided for all AEs, SAEs, AEs leading to study medication discontinuation, AEs leading to death, AEs related to COVID-19, and SAEs related to COVID-19.

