3.2 Rationale for Study Design and Control Group

Current treatment options for FCD include hyperosmotic saline ophthalmic drops/ointments and surgical procedures. Hyperosmotic saline can provide temporary symptomatic relief by facilitating corneal dehydration. Endothelial keratoplasty using donor corneas is currently the gold standard therapeutic option to restore vision in patients with FCD. Although improvement of surgical techniques has enabled less invasive treatment and better outcomes, corneal transplants require long-term steroid use and are still associated with difficult surgical techniques, graft rejection, acute/chronic cell loss, and worldwide donor cornea shortages ([Okumura 2017](#)). A relatively new non-transplant surgical procedure known as Descemet Stripping Only (DSO) or Descemetorhexis Without Endothelial Keratoplasty (DWEK) is also now available for a minority of FCD patients.

A pharmacologic alternative to surgery in patients with FCD would be very beneficial, even if pharmacologic treatment only delays the need for surgery.

This study is designed to investigate the efficacy and safety of netarsudil for the treatment of FCD and to enable optimal study design for further clinical development. The optimal dosing regimen will provide maximum reduction in corneal edema due to FCD with minimal adverse effects.

It should be noted that, since FCD is a slowly progressing disease, surgery is rarely urgent, and patients are often seen multiple times before undergoing surgery. Therefore, an approximate 8 to 9-week delay in surgery for participation in this study is acceptable.

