## 4. Study Treatments

### 4.1 Treatment Administered

Subjects will be randomized using a 1:1 allocation ratio to one of two treatment groups:

- Netarsudil QD Dosing Regimen
  - Study Artificial Tear: one drop in the study eye in the morning
  - Netarsudil 0.02% ophthalmic solution: one drop in the study eye in the evening
- Netarsudil BID Dosing Regimen
  - Netarsudil 0.02% ophthalmic solution: one drop in the study eye in the morning and in the evening

Doses will be self-administered by the study subjects. If the subject is using any another topical ophthalmic drop (e.g., ocular hypotensive medications) at the same time as netarsudil, the subject should be instructed to instill netarsudil first, and wait at least 15 minutes before instilling any additional drops.

For subjects deemed unable to self-administer the doses, a caregiver will be asked to administer the medication. All subjects will administer study medication for approximately 8 weeks.

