## 5. Sample Size and Power Considerations

This study is not powered to detect a pre-stated efficacy signal, but rather will be used to inform the design and power for any possible future studies. With a sample size of up-to 20 subjects per treatment group, the precision of the point estimate of mean change from baseline in CCT, as measured by the half-width of the two-sided 90% confidence interval (CI), will be approximately  $1/2.7$  of the standard deviation (SD) of the change from baseline, yielding 90% confidence that the true mean change from baseline is within  $\pm SD/2.7 \mu\text{m}$  of the observed mean change from baseline. That is, if the SD of the change from baseline is  $60 \mu\text{m}$ , then the half-width of the two-sided 90% CI would be  $60 \mu\text{m} \times 1/2.7 = 22.2 \mu\text{m}$ , yielding 90% confidence that the true mean change from baseline is within  $\pm 22.2 \mu\text{m}$  of the observed mean change from baseline.

With a sample size of up-to 20 subjects within a treatment group, the study will have 80% power to reject  $H_{01}$  or  $H_{02}$  and in favor of  $H_{11}$  or  $H_{12}$  respectively and demonstrate a statistically significant mean change from baseline, assuming the true effect size (mean change / SD) is 0.577 or larger (e.g. assuming the true mean change from baseline is  $34.6 \mu\text{m}$  and the SD is  $60 \mu\text{m}$ ), a one sample t-test and a two-sided alpha = 0.10.

With a sample size of up-to 20 subjects per treatment group, the study will have 95% confidence of ruling out AEs with true incidence rates of 13.9% or higher within each treatment group. That is, with up-to 20 subjects in a treatment group, if an AE of a specific type is not observed, then with 95% confidence, the true incidence rate of that adverse event is less than 13.9%.

Similarly, with a sample size of up-to 40 subjects combined over treatment groups, the study will have 95% confidence of ruling out AEs with true incidence rates of 7.2% or higher within each treatment group. That is, with up-to 40 subjects in a treatment group, if an AE of a specific type is not observed, then with 95% confidence, the true incidence rate of that AE is less than 7.2%.

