## 13. Safety Analyses

All safety analyses will be conducted using the safety population. For visit-based safety summaries (BCVA, biomicroscopy, IOP, and vital signs), subjects who switched dose group from QD to BID starting from Week 4 will be reported under treatment group BID at Week 8 visit. The baseline value for these subjects will remain the same.

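### If any QD subject moves to BID at Week 4, the 8-week adverse-event percentages for QD and BID are not comparable, and no planned table compares the randomised arms over equal exposure

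*SAP*

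**What the plan says.** Subjects are allocated 1:1 to QD or BID for about 8 weeks (SAP 4.1). At Week 4 the investigator may move a QD subject whose response is judged inadequate to BID; there is no change in the other direction (SAP 3.1, Protocol 3.1).

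For every adverse-event table, SAP 13.1 says that "a third group other than QD and BID dose group will be presented to capture the AEs for those subjects who switched". It then attributes events by dose at onset:

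- For new events after the change: "The AE that began on or after the switch will be considered treatment emergent to the BID treatment".
- Events that began earlier and continue belong to QD only.
- Events that worsen after the change are split, with the worse episode attributed to BID and the original to QD.

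The tables give event counts and numbers and percentages of subjects. SAP 13.1 states no denominator for any column, describes no person-time, and the table list in SAP 18 has no exposure table.

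The visit-based safety summaries follow a different rule (SAP 13): "subjects who switched dose group from QD to BID starting from Week 4 will be reported under treatment group BID at Week 8 visit".

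**The concern.** A subject who switches has about 4 weeks on QD and then 4 on BID, while a subject randomised to BID has 8 weeks on BID. A crude percentage depends on how long subjects are observed, so columns with different exposure cannot be read against each other. Switchers are also chosen after randomisation, on response, so removing them from QD or adding them to BID means that column is no longer a randomised group.

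The SAP does not say whether the BID treatment in the onset rule means the BID column or the BID part of the third group. Nor does it say where switchers' QD-period events are shown. Each answer gives a different pair of percentages from the same data.

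This matters because Protocol 3.2 ties the choice of regimen to tolerability: "The optimal dosing regimen will provide maximum reduction in corneal edema due to FCD with minimal adverse effects". With about 20 subjects per arm and no planned test, the descriptive percentages are the main safety evidence on regimen.

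**Working it through.** **The plan's own safety figure.** SAP 5 says "With a sample size of up-to 20 subjects per treatment group, the study will have 95% confidence of ruling out AEs" above a stated rate, and that if none is seen "the true incidence rate of that adverse event is less than 13.9"%. The exact zero-event bound is 1 − 0.05^(1/n). For n = 20 this is 13.9%; for n = 40 it is 7.2%. Both stated figures reproduce, but they presuppose that each subject contributes the full observation period.

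**Inputs.** From the documents: 20 subjects per arm, 8 weeks, change possible at Week 4. The documents give no switch rate, event rate or time course. Assumed: the same constant hazard under both regimens, 8-week risk p8 = 40%, m = 6 of 20 QD subjects switching (30%), and no dropout.

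**Step 1: 4-week risk.** p4 = 1 − √(1 − p8) = 1 − √0.60 = 22.5%.

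**Step 2: exposure.** QD time is 14 × 8 + 6 × 4 = 136 person-weeks. Subjects randomised to BID contribute 20 × 8 = 160.

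**Step 3: what the columns show with no true difference.**

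| Layout | QD column | BID column |
|---|---|---|
| A. Pre-switch events in QD; post-switch events in the third group only | (14 × 0.40 + 6 × 0.225)/20 = 6.95/20 = 34.8% | 8/20 = 40.0% |
| B. As A, but post-switch events join BID and switchers join its denominator | 34.8% | (8 + 6 × 0.225)/26 = 9.35/26 = 36.0% |
| C. Switchers appear only in the third group | 5.6/14 = 40.0% | 40.0% |

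The gap is 5.2 points in A and 1.2 in B. In C there is no exposure gap, but QD holds only the 14 subjects not judged to need a change, set against all 20 on BID.

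**Step 4: sensitivity.**

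- *Ten switchers instead of six:* QD time is 10 × 8 + 10 × 4 = 120 person-weeks. QD in layout A is (4 + 10 × 0.225)/20 = 31.3% against 40%.
- *Event risk of 30%, ten switchers:* the layout A gap is 6.8 points.
- *All events in Weeks 0 to 4:* layout A shows 40% in both columns. Layout B shows 40% for QD and 8/26 = 30.8% for BID, so the sign reverses.

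**Step 5: effect on the plan's bound.** With no events seen on QD, the bound on the 8-week rate under constant hazard is 1 − 0.05^(8/person-weeks). With 136 person-weeks it is 16.2%, and with 120 it is 18.1%, against the stated 13.9%.

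**The case against.** The strongest case on the other side is that this is an unclear table layout, not a demonstrated bias. Much of that stands.

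- **Double counting.** A reader might infer from the two sentences in SAP 13.1 that post-switch events appear in both the BID and the third column. The SAP does not say so. Its wording also fits a single count inside the third group, labelled by dose at onset. SAP 12.3 and 12.5 likewise report switchers in a separate group at Week 8 in the per-protocol and ad-hoc efficacy tables.
- **An inflated BID percentage.** If post-switch events entered BID with its denominator left at 20, BID would show 9.35/20 = 46.8%. No stated denominator supports that layout, so this figure should not be used as the size of the problem.
- **Direction.** A reader might conclude that QD will look safer. Step 4 shows that the sign depends on layout and event timing, and the documents settle neither.
- **The Week 8 rule in SAP 13.** It covers only BCVA, biomicroscopy, IOP and vital signs. It does not establish a pooled BID column for adverse events, though it does mean that BID may describe different subjects in different safety tables.
- **Scale and use.** A gap of 34.8% against 40% is about one subject in 20, and the exact 95% interval for 8 of 20 is roughly 19% to 64%. The summaries are descriptive, Protocol 3.2 is a rationale and not a selection rule, and subject listings will be available.

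This does not remove the central point. The layout without an exposure gap gets there by conditioning QD on a decision made after randomisation. A systematic distortion remains a distortion when the sample is small, and none of the planned tables avoids it.

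**Conclusion.** The concern holds on comparability. If at least one QD subject switches, the 8-week QD and BID columns have unequal exposure, are no longer the randomised groups, or both. No planned adverse-event table compares the randomised arms over equal exposure. With equal constant hazard, 40% 8-week risk and 30% switching, the spurious gap is 5.2 points, 1.2 points or nil, depending on the layout. Those sizes rest entirely on assumed rates. If nobody switches, the problem does not arise.

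The documents do not support a claim that events are counted twice, or that the bias has a known direction. No formal inference is affected, because no between-regimen test of adverse events is planned. The Week 4 dosing rule itself is not in question here.

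**What to change.** In SAP 13.1:

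1. Add a table of treatment-emergent events by randomised arm, restricted to onset before the Week 4 visit dose change, and name it as the QD versus BID comparison. Apply the same cut-off in both arms and state it for subjects with no Week 4 visit. Planned exposure is then equal and randomisation is intact.
2. State the column and the denominator for switchers' pre-switch and post-switch events, and count each event once. Reconcile this with the visit-based rule in SAP 13, or explain why the two differ.
3. Show person-weeks and events per person-week by column in the 8-week tables. Under equal constant hazard these rates agree whatever the layout. They do not correct for events that cluster early or for selection of switchers, so item 1 remains the main comparison.

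The cost is one extra table and added exposure and rate rows, using data already collected. The downside is that events starting after Week 4 fall outside the randomised comparison and are read only from the 8-week tables. All adverse-event summaries remain descriptive.

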### 13.2 Best Corrected Visual Acuity

BCVA testing using ETDRS will be performed at all scheduled visits for both eyes. BCVA will be presented as letter score and logMAR. The observed and change from baseline values will be summarized for each eye (study eye and fellow eye) using continuous summary statistics by visit for each treatment group. A subject listing of visual acuity will also be provided.

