In addition to lowering intraocular pressure, ROCK inhibitors, such as netarsudil, may also have potential benefit for the treatment of corneal endothelial decompensation. Although the mechanisms are still being elucidated, preclinical evidence is emerging that ROCK inhibition can promote adhesion, enhance proliferation, and inhibit apoptosis of corneal-endothelial cells ([Okumura 2009](#), [Okumura 2017](#)). Findings from a clinical case series suggest that topical administration of the ROCK inhibitor Y-27632 after performing transcorneal freezing can improve central corneal edema in patients with FCD ([Okumura 2013](#)). In one patient, full corneal transparency was achieved for more than 6 years, and original plans for corneal transplantation were cancelled ([Koizumi 2013](#), [Okumura 2018](#)). An additional two case reports of patients with FCD have described improvements in corneal edema and corneal endothelial cell counts with the use of netarsudil following DSO ([Ploysangam 2019](#), [Hirabayashi 2020](#)). Several clinical trials are now ongoing to investigate ROCK inhibition in both pre-surgical (NCT04051463) and post-surgical (NCT03575130, NCT03813056, NCT03249337, NCT03971357, NCT04250207, NCT04057053) FCD patients.

Overall, netarsudil is well tolerated, and the most common adverse event is conjunctival hyperemia. Several case reports of honeycomb or reticular edema have been observed in patients taking netarsudil, both with and without pre-existing corneal edema or a history of

FCD ([Fernandez 2018](#), [Liu 2019](#), [Moumneh 2020](#), [Wisely 2020](#)). Typically, reticular or honeycomb edema resolves after discontinuation of netarsudil.

The aim of this study is to evaluate the therapeutic potential of netarsudil as a pharmacologic agent to delay or prevent the need for surgery in patients with visually significant edema due to FCD.

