4.2 Inclusion Criteria

Subjects must meet all of the following criteria to enter into the study:

1. Adults, aged 18 years or older at the Screening Visit, of either sex and any race or ethnicity
2. Documented diagnosis of FCD at the Screening Visit
3. Evidence of central corneal edema, in at least one eye, at the Screening and Baseline Visit. The study eligible eye(s) should have a CCT of at least 600 μm at both Screening and Baseline, as assessed by ultrasound pachymetry
4. Evidence of corneal edema attributed to FCD of <12-months' duration in the eligible eye(s)
5. Best Corrected Visual Acuity using the Early Treatment of Diabetic Retinopathy Study (ETDRS) methodology of 70 to 20 letters at Screening and Baseline in the eligible eye(s)
6. Presence of central corneal edema deemed by the Investigator to be the chief cause of reduced visual acuity in the eligible eye(s)
7. Willing and able to provide written informed consent to participation in the study prior to any and all study-related activities

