9.8.5 Exploratory Efficacy Endpoints

Exploratory endpoints include:

- Proportion of subjects who gained ≥ 15 letters (3 lines) in BCVA at Week 2
- Proportion of subjects who gained ≥ 10 letters (2 lines) in BCVA at Weeks 2, 4, and 8
- Proportion of subjects who gained ≥ 5 letters (1 line) in BCVA at Weeks 2, 4, and 8
- Mean change from baseline in CCT as assessed by Pentacam® at Week 4 (selected sites only)
- Mean change from baseline in V-FUCHS glare factor score at Week 4

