9.8.7 Primary Safety Assessments and Analyses

Adverse events (AEs) will be coded using the MedDRA dictionary. Frequencies and percentages of treatment-emergent adverse events (TEAEs) will be summarized at the subject level by system organ class and preferred term for all TEAEs, treatment related TEAEs, serious TEAEs, and TEAEs causing premature treatment discontinuation by treatment group. An AE is treatment emergent if it occurs or worsens after the first dose of study medication. Similar summaries will be presented for all TEAEs by maximal severity. Separate summaries will be performed for ocular and non-ocular AEs.

Best corrected visual acuity and intraocular pressure data for both the study eye and the fellow eye will be summarized for each measured visit and for change from baseline to each post-treatment visit using the continuous summary statistics.

Anterior segment biomicroscopy and ophthalmoscopy measures will be summarized at each measured visit using discrete summary statistics. Additionally for anterior segment biomicroscopy, discrete summaries will be provided by region, finding, visit, time point, and eye (study eye and fellow eye) for the number of subjects with at least one severity grade increase from baseline and for the number of subjects judged to be clinically significant by the Investigator. Shift tables from baseline may also be summarized.

Vital signs will be summarized at each measured visit and for change from baseline to each measured visit using continuous summary statistics by treatment group and visit.

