### 2.2 Safety

The safety of netarsudil QD and BID will be evaluated by:

- Adverse events (AEs)
- BCVA
- Anterior segment biomicroscopy
- Intraocular pressure (IOP)
- Ophthalmoscopy
- Vital signs (heart rate and blood pressure)

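### BCVA is a named safety measure and letter gains are tabulated at three thresholds, but no planned summary table counts subjects who lose letters

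*SAP*

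**What the plan says.** SAP 2.2 and the protocol synopsis both name BCVA as a safety assessment, and the safety of each regimen is the second secondary objective.

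SAP 13.2 sets out the safety analysis of BCVA: "The observed and change from baseline values will be summarized for each eye (study eye and fellow eye) using continuous summary statistics by visit". It adds: "A subject listing of visual acuity will also be provided". SAP 8.4 defines the continuous statistics as n, mean, median, SD, minimum and maximum. Protocol 9.8.7 is to the same effect: "Best corrected visual acuity and intraocular pressure data for both the study eye and the fellow eye will be summarized for each measured visit", again with continuous statistics. Table 14.3.3.1 is the only BCVA table in the safety part of the SAP's table list. The protocol synopsis allows for shifts from baseline where appropriate, but SAP 13.2 plans none for BCVA.

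On the efficacy side, subjects who gain at least 15, 10 and 5 letters are counted by regimen and visit, for example "Proportion of subjects who gained ≥ 5 letters (1 line) in BCVA at Weeks 2, 4, and 8" in protocol 9.8.5. These counts fill six tables, 14.2.3.1.1 to 14.2.3.3.2, and SAP 12.3 and 12.4 also test them between regimens.

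The protocol introduction gives a reason to look in the other direction: "Several case reports of honeycomb or reticular edema have been observed in patients taking netarsudil, both with and without pre-existing corneal edema". It adds that such edema typically resolves once netarsudil is stopped. Inclusion criterion 6 requires central corneal edema to be, in the investigator's judgement, the main reason for poor acuity in the eligible eye.

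**The concern.** In this population the hoped-for benefit and the reported adverse finding can move the same measure in opposite directions. Less edema should raise the letter score, and treatment-associated edema should lower it. A mean change adds the two together. The gain tables show one tail of the distribution at three cut-points, and nothing shows the other tail.

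Protocol 3.2 wants the study to help identify a regimen that reduces edema most with the fewest adverse effects, and to inform later trials. How many subjects on each regimen finished a visit with materially worse vision than at baseline is a basic safety figure for that purpose. As planned, it would have to be counted by hand from the listing.

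**Working it through.** **The plan's own safety figure.** SAP section 5 reasons in terms of subject-level incidence. With 0 events in n subjects the one-sided 95% upper bound is 1 - 0.05^(1/n). For n = 20 this is 13.9% and for n = 40 it is 7.2%, as stated. A count of subjects losing letters would fit directly into that reasoning; a mean change does not.

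**Where worsening is counted now**

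| Measure | Worsening tabulated? | Place |
|---|---|---|
| Stromal and epithelial edema grade | Yes: shifts, and subjects worse by at least one grade | SAP 12.1.3, 13.3 |
| Ocular adverse events | Yes: by eye, preferred term, relationship and severity | SAP 13.1 |
| BCVA letters | No: continuous statistics and a listing | SAP 13.2, Table 14.3.3.1 |

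**Can the planned statistics recover the number of losers?** Take two constructed sets of 20 letter changes (illustrative, not trial data):

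- Set A: -20; -14 (five subjects); -10 (two); 0; 3 (two); 8; 10 (two); 15 (three); 20 (three).
- Set B: -20 (two); -15 (four); -5; 0 (three); 6; 10 (two); 12 (four); 20 (three).

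In both, the sum is 29 and the sum of squares is 3737. So the mean is 29/20 = 1.45 and the SD is sqrt((3737 - 29²/20)/19) = 13.95. The median is (3 + 3)/2 = 3 in A and (0 + 6)/2 = 3 in B. The minimum is -20 and the maximum 20 in both. Yet 1 subject in A and 6 in B lost at least 15 letters.

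The gain tables would differ between the sets but would not fill the gap. Gains of at least 5, 10 and 15 letters number 9, 8 and 6 in A, and 10, 9 and 3 in B. Subjects without a 5-letter gain number 20 - 9 = 11 in A and 20 - 10 = 10 in B, so B has one fewer non-gainer although five more lost 15 letters. Non-gainers mix unchanged and worsened subjects.

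**A simpler case (assumed values; the documents give no loss rate).** If 17 subjects gain 8 letters and 3 lose 15:

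- mean = (17 × 8 - 3 × 15)/20 = 91/20 = 4.55; median 8; minimum -15;
- SD = sqrt((17 × 64 + 3 × 225 - 91²/20)/19) = sqrt(1348.95/19) = 8.43;
- one-sample t = 4.55/(8.43/sqrt(20)) = 2.41 on 19 df, two-sided p = 0.026, in favour of improvement.

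With one such loser instead of three, the minimum is still -15 and the median still 8.

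**What the added rows would show for an arm of 20**

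| Losers | Percentage | Exact two-sided 95% CI |
|---|---|---|
| 1 | 5% | 0.1% to 24.9% |
| 2 | 10% | 1.2% to 31.7% |
| 3 | 15% | 3.2% to 37.9% |

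For 0 losers the one-sided 95% upper bound is the plan's own 13.9%. For a comparison of arms, 3/20 against 0/20 gives a two-sided Fisher p of 2 × (20·19·18)/(40·39·38) = 0.23.

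**The case against.** The strongest reply is that the harm named in the protocol is edema, and edema is counted. Stromal and epithelial edema are graded in both eyes at every scheduled visit, with shift tables, counts of subjects who worsen by a grade and counts of findings judged clinically significant. This stands: a reader might infer that the number of eyes harmed appears nowhere, and the documents do not support that. But a slit-lamp grade is not acuity. Adverse event tables depend on what the investigator chooses to report in an open-label study, and neither document sets a letter loss that must be recorded as an event.

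Second, the minimum is planned and every subject's BCVA is listed in a trial of about 40. So it would be wrong to infer that only means are reported, or that a large loss could pass unseen. What is missing is the count by regimen. The gains could equally be read from a listing, yet they are given six tables.

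Third, the gain counts follow from the first secondary objective, which concerns improvement in vision. That explains why they are there; it does not answer the second objective, safety.

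Fourth, small losses may be measurement noise. That applies equally to the planned 5-letter gain table, and showing both directions helps the reader judge it.

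**Conclusion.** The gap is real but limited to reporting. BCVA loss is the only part of this safety picture without a subject-level count, and the example shows that n, mean, SD, median, minimum and maximum can leave 1 and 6 losers indistinguishable. The primary analysis is unaffected. The letter changes used are assumptions, so the example shows what the tables cannot reveal, not what the trial will find.

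Three further inferences are not supported:

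- **That CCT is reported one-sidedly too.** The SAP has no CCT responder table in either direction. A count of corneas thicker than baseline would mostly reflect ordinary variation. With the plan's example (mean reduction 34.6 µm, SD 60 µm) and a normal distribution, Φ(-34.6/60) is about 28% of eyes in an arm that works as hoped; with no effect it would be 50%.
- **That loss counts would separate QD from BID.** Even 3/20 against 0/20 gives p = 0.23, so the rows can only be descriptive.
- **That the protocol states netarsudil causes edema.** It reports cases observed in patients taking it.

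**What to change.** In SAP 13.2 and Table 14.3.3.1, add by regimen, visit and eye the number and percentage of subjects who lost at least 5, 10 and 15 letters from baseline, with an exact confidence interval for the study eye. Use subjects with a baseline value and a value at that visit as the denominator, and label the rows descriptive.

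State a Week 8 rule for these rows. SAP 13 places subjects moved from QD to BID under BID at Week 8 in visit-based safety summaries and leaves their baseline unchanged. Letters lost during the QD weeks would then be counted against BID, and those who move are the subjects judged not to have responded adequately on QD. Show them as a separate QD-to-BID group, as SAP 13.1 does for adverse events and SAP 12.3 for the per-protocol summaries.

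No CCT-above-baseline count is needed. The cost is a short SAP edit and some extra rows in an existing table, from data already collected; no visit, assessment or treatment rule changes.
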